8. TREATMENT OF SUBJECTS

8.1. Description of Study Drug

MN-166 and matching-placebo will be provided in bottles containing MN-166 10 mg capsules or matching-placebo capsules, and will be stored at room temperature.

8.2. Concomitant Medications

Subjects may continue the use of IFN- β or glatiramer acetate while participating in this study. During the study, subjects may be allowed to change medications from one injectable to the other. Pegylated interferon beta-1 will be allowed (if approved by the FDA).

Inhaled and topical steroids are allowed.

If a relapse episode occurs, a single course of systemic corticosteroids is permitted, as prescribed by the treating neurologist.

8.3. Prohibited Medications

The following medications are **prohibited** prior to and during study participation:

- Systemic corticosteroid treatment within 3 months prior to screening (inhaled or topical steroids are allowed).
 - A single course of systemic corticosteroid treatment will be allowed for treatment of a clinical relapse
- Current use of intermittent systemic corticosteroids (i.e., monthly or bimonthly intravenous methylprednisolone)
- Oral immunosuppressants (e.g., azathioprine, methotrexate, cyclosporine, teriflunomide [Aubagio[®]]) within 6 months of screening
- Mitoxantrone or natalizumab within 6 months of screening
- Fingolimod or dimethyl fumarate [Tecfidera[®]] within 3 months of screening
- Rituximab or other B-cell therapy within 12 months of screening
- Current use of other MS disease-modifying therapies (DMTs) besides glatiramer acetate and IFN β -1 (any formulation).

The following medications are prohibited during study participation:

- cimetidine, cyclosporine, dronedarone, lopinavir, probenecid, quinidine (including Neudexta), ranolazine, rifampin, ritonavir, or tipranavir

8.4. Treatment Compliance

Compliance will be monitored closely at each visit. Subjects will be instructed to bring all unused study medication with them to each visit for drug accountability. Compliance will be assessed at weeks 24, 72, and 96 by counting capsules and dividing the actual number of doses taken (per capsule count) by the number of days the subject took study drug. All subjects will be reminded of the importance of strict compliance with taking study medication for the effectiveness of treatment and for the successful outcome of the study. Subjects who miss more than 25% of scheduled doses or take more than 125% of the scheduled doses will be considered noncompliant and may be discontinued from the study per investigator's judgment.

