6.1.2. Treatment Phase (96 weeks)

The double-blind Treatment Phase consists of a Baseline visit followed by 10 scheduled clinic visits. The Baseline Visit must occur within 45 days following the Screening Visit. At the Baseline Visit (Day 1), subjects who have completed all of the screening assessments and continue to meet eligibility criteria will be randomized to one of two treatment groups (MN-166 100 mg/d or placebo) in a 1:1 ratio.

Subjects will take their first dose of study medication (30 mg MN-166 or placebo) on the evening of the Baseline Visit (Day 1). On the morning of Day 2, all subjects will begin a 3 capsule BID dosing regimen through Day 14. Subjects randomized to MN-166 will start at 60 mg/d (30 mg BID) on Day 2 and will remain on 60 mg/d through Day 14. Beginning on Day 15, all subjects will increase dosing to 5 capsules BID regimen; those randomized to the MN-166 treatment arm will be taking 100 mg/d.

After Day 15, subjects with intolerable side-effects (e.g., nausea, diarrhea, vertigo) may reduce their dose to either 4 capsules twice a day (80 mg/d for those taking ibudilast) or 3 capsules twice a day (60 mg/d for those taking ibudilast). Subject with intolerable side-effects (e.g., nausea, diarrhea, vertigo) at the end of Day 14 may continue to taking 3 capsules twice a day at the investigator's discretion. At the investigator's discretion, the daily dose of ibudilast can be changed between 3 capsules twice a day, 4 capsules twice a day, and 5 capsules twice a day over the first 8 weeks of treatment. At the investigator's discretion, the daily dose of ibudilast may be divided and taken three times per day if needed to improve tolerability. At the end of the first 8 weeks of treatment, the subject must maintain their then-current daily dose of study medication (6 capsules per day, 8 capsules per day, or 10 capsules per day). The dosing interval may be twice a day or 3 times per day, at the investigator's discretion. The dosing interval may be changed between twice and three times per day over the course of the entire study, at the investigator's discretion.

Subjects will return to the clinic for follow-up visits on a regular basis at Week 4, 8, 12, 24, 36, 48, 60, 72, 84 and 96 (see Table 1: Schedule of Assessments).

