- BPI
- SF-36
- MSIS-29
- EQ-5D
- SBQ-R
- Hematology, chemistry, lipid profile, and urinalysis labs
- Serum biomarker samples
- Serum pregnancy test (in females)
- Plasma sample for PK
- ECG (12-lead)
- MSFC
- EDSS by blinded neurologist
- Brain MRI
- OCT

- Lumbar puncture (optional)
- Return of used/unused study drug bottles, study drug accountability and compliance check
- Dispense study drug

Study Visit 9 (Week 60)

- Physical examination
- Body weight
- Vital signs
- Interval history
- Adverse event review
- Concomitant medication review
- Relapse assessment
- BPI
- SBQ-R
- Hematology, chemistry, and urinalysis labs
- Serum pregnancy test (in females)
- ECG (12-lead)
- Study drug accountability

Study Visit 10 (Week 72)

- Physical examination
- Body weight
- Vital signs
- Interval history
- Adverse event monitoring
- Concomitant medication review
- Relapse assessment
- Cognitive tests (SDMT and the SRT)
- BPI
- SF-36
- MSIS-29

- EQ-5D
- SBQ-R
- Hematology, chemistry, and urinalysis labs
- Serum pregnancy test (in females)
- ECG (12-lead)
- MSFC
- EDSS by blinded neurologist
- Brain MRI
- OCT
- Return of used/unused study drug bottles, study drug accountability and compliance check
- Dispense study drug

Study Visit 11 (Week 84)

- Physical examination
- Body weight
- Vital signs
- Interval history
- Adverse event review
- Concomitant medication review
- Relapse assessment
- BPI
- SBQ-R
- Hematology, chemistry, and urinalysis labs
- Serum pregnancy test (in females)
- ECG (12-lead)
- Study drug accountability

Study Visit 12 (Week 96)

- Physical examination
- Body weight
- Vital signs

- Interval history
- Adverse event monitoring
- Concomitant medication review
- Relapse assessment
- Cognitive tests (SDMT and SRT)
- BPI
- SF-36
- MSIS-29
- EQ-5D
- SBQ-R
- Hematology, chemistry, lipid profile, and urinalysis labs
- Serum biomarker samples
- Serum pregnancy test (in females)
- Plasma sample for PK
- ECG (12-lead)
- MSFC
- EDSS by blinded neurologist
- Brain MRI
- OCT
- Lumbar puncture (optional)
- Return of used/unused study drug bottles, study drug accountability and compliance check

Follow-up Visit 13 (Week 100)

- Physical examination
- Body weight
- Vital signs
- Interval history
- Adverse event monitoring
- Concomitant medication review
- Relapse assessment
- SBQ-R

Unscheduled Visits**Relapse Evaluation**

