6.1. Primary and Major Secondary Efficacy Analyses

6.1.1. Modified Intent-to-Treat (mITT) Population

The primary analysis for all primary and major secondary efficacy objectives will be implemented using a modified intent-to-treat (mITT) approach, which is defined as all subjects who are:

- Randomized
- Received at least one dose of study medication
- Have at least one efficacy assessment (i.e., week 24, 48, 72, or 96 visit) during the double-blind phase of the study

All subjects meeting this criteria will be analyzed based on the treatment to which they were randomized, whether or not they remained compliant with respect to taking study medication.

6.1.2. Per Protocol (PP) Population:

To assess the sensitivity of the results, and to obtain knowledge regarding the potential effects when the protocol was strictly adhered to, we will also replicate all primary and major secondary efficacy objectives using a per protocol population. The per-protocol population includes the subset of all mITT subjects who satisfy both of the following conditions:

- Have 75% -125% compliance (both limit values inclusive) with assigned study medication as randomized in the double-blind phase
- Have no major protocol deviations (defined as any alteration/modification to the protocol that has the potential to negatively impact subject safety, integrity of the study, ability to draw conclusions from the study data, or affect the subject's willingness to participate in the study)

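### Compliance has two unreconciled denominators, and the choice decides whether a patient who stops drug before about Week 72 can meet the per-protocol compliance criterion

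*Combined protocol and SAP*

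**What the plan says.** - **Formula.** Protocol 8.4 computes compliance by "dividing the actual number of doses taken (per capsule count) by the number of days the subject took study drug".
- **Limits.** A little later the same section says "Subjects who miss more than 25% of scheduled doses or take more than 125% of the scheduled doses will be considered noncompliant". It does not say whether scheduled doses run to the stop date or to Week 96.
- **Timing.** Protocol 8.4 states "Compliance will be assessed at weeks 24, 72, and 96". The Week 48 visit list in protocol 8.8.1.2 also includes "Return of used/unused study drug bottles, study drug accountability and compliance check".
- **Per-protocol set.** SAP 6.1.2 requires that subjects "Have 75% -125% compliance (both limit values inclusive) with assigned study medication as randomized in the double-blind phase" but gives no formula and does not refer to protocol 8.4. The second condition is "Have no major protocol deviations (defined as any alteration/modification to the protocol that has the potential to negatively impact subject safety", with further grounds listed. Protocol 12.1.1 leaves that judgement to a blinded data review. Neither document names early drug discontinuation as a per-protocol exclusion.
- **Purpose.** SAP 6.1.2 repeats all primary and major secondary efficacy analyses in this set, to learn what the effect is under strict adherence.
- **Dose levels.** Protocol 6.1.2 allows maintenance at "6 capsules per day, 8 capsules per day, or 10 capsules per day".
- **After stopping drug.** Protocol 7.3.1 and the semi-annual visit list in 8.8.1.2 keep these patients in follow-up at Weeks 24, 48, 72 and 96, with brain MRI. One such visit is enough for the mITT set (SAP 6.1.1), from which the per-protocol set is drawn.

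**The concern.** Doses divided by days is a rate, so it cannot be compared with 75%–125% until a reference dose is supplied. Once it is, the denominator stops growing when the patient stops drug. A patient with good intake for a few months and none afterwards can then look fully compliant.

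The alternative wording in the same section, scheduled doses, gives a very different score if the schedule runs to Week 96. The SAP does not choose between them. Two analysts working from the same text could build different per-protocol sets, and one version would include scans taken long after drug was stopped. That works against the stated purpose of the set and tends to pull the estimated slope difference towards zero.

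**Working it through.** The documents report no compliance result or per-protocol count, so there is no figure to reproduce. The check counts capsules.

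**Schedule** (protocol 6.1.2 and 8.6.1; 96 weeks = 672 days): 3 capsules on Day 1, 6 per day on Days 2–14, 10 per day from Day 15.

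Total = 3 + 13 × 6 + 658 × 10 = 3 + 78 + 6,580 = **6,661 capsules**.

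**Two scores for a full-dose patient who takes every capsule until stopping:**

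- A = capsules taken / capsules due while on drug (the protocol 8.4 formula, with scaling to the scheduled dose added as an assumption)
- B = capsules taken / 6,661

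| Stop at | Days | Capsules taken | Capsules per day on drug | A | B |
|---|---|---|---|---|---|
| Week 12 | 84 | 81 + 70 × 10 = 781 | 9.30 | 100% | 11.7% |
| Week 24 | 168 | 81 + 154 × 10 = 1,621 | 9.65 | 100% | 24.3% |
| Week 48 | 336 | 81 + 322 × 10 = 3,301 | 9.82 | 100% | 49.6% |
| Week 72 | 504 | 81 + 490 × 10 = 4,981 | 9.88 | 100% | 74.8% |
| Week 84 | 588 | 81 + 574 × 10 = 5,821 | 9.90 | 100% | 87.4% |

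**Crossing point.** 75% of 6,661 is 4,995.75 capsules. Day 505 gives 81 + 491 × 10 = 4,991 and Day 506 gives 5,001. So 75% is first reached on Day 506 (Week 72.3). Any such patient stopping earlier passes on A and fails on B; later stoppers pass on both.

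**Dose reference.** Against a fixed 10 per day from Day 15, a patient held at 6 per day scores (81 + 658 × 6)/6,661 = 4,029/6,661 = 60.5%. One held at 8 per day scores (81 + 658 × 8)/6,661 = 5,345/6,661 = 80.2%. Against the assigned level both score 100%.

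**Possible dilution, under stated assumptions.** Assume that the benefit on slope ends at the stop, that every stopper stays in follow-up and passes the criterion, and that an ordinary least-squares slope over Weeks 0, 24, 48, 72 and 96 approximates the mixed model. A stopper at Week 24 then retains 0.20 of the slope effect and one at Week 48 retains 0.50. With stops spread evenly over 96 weeks the mean retained share is 0.50.

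- 14% stopping, spread evenly: 0.14 × 0.50 = 7% relative loss. A 35% slowing would appear as 35 × 0.93 = 32.6%.
- 10% stopping, spread evenly: 0.10 × 0.50 = 5%, giving 33.3%.
- 14% all stopping at Week 24: 0.14 × 0.80 = 11.2%, giving 31.1%.

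The 14% is 100% minus the 86% two-year completion of the 60 mg/d group in the earlier relapsing-remitting trial (protocol 4.6.3). The 10% is this trial's planning dropout (protocol 12.1.3, SAP 9.1). Neither is a rate of stopping drug while remaining in follow-up.

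**The case against.** A reader might infer that early stoppers always count as compliant and always stay in the per-protocol set. The documents do not support that.

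- The limits in protocol 8.4 refer to scheduled doses, and SAP 6.1.2 asks for compliance over the double-blind phase, which lasts 96 weeks. Read together, these would exclude a full-dose patient who stops before about Week 72.
- The blinded review of major deviations could remove others, since the SAP definition reaches anything that impairs conclusions from the data. Stopping drug and staying in follow-up is a planned path, however, so it is not plainly a deviation.
- The 100% score needs a scaling step that the protocol does not state.

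These objections stand. Early stoppers can score about 100%, but need not. What survives is that the only written formula excludes off-drug time, and nothing in the text settles which reading governs.

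A reader might also infer that "with assigned study medication as randomized in the double-blind phase" fixes 10 capsules per day as the reference, so that patients on a permitted lower level are dropped. No section says so. Assigned arm is the more natural reading, and a margin comment in protocol 12.1.1 treats that phrase as redundant with the compliance condition. The wording needs clarifying; it does not show that anyone would be wrongly excluded.

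The Week 48 mismatch is a minor conflict with no demonstrated effect on any patient's score.

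The dilution figures are also open to challenge. Patients who leave the study contribute no off-drug scans, and those with no Week 24–96 assessment are not in the mITT set at all.

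**Conclusion.** The point holds as an unresolved definition. Protocol 8.4 contains two denominators and the SAP adopts neither. The choice reverses the compliance criterion for every full-dose patient with perfect intake who stops before Day 506, for example 100% against 24.3% for a stop at Week 24.

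The effect is confined to the per-protocol sensitivity analysis. The primary mITT analysis keeps patients whatever their compliance, so it should not be inferred that the main result is at risk.

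The effect on the per-protocol estimate cannot be fixed from the documents, because they do not give the number of stoppers who remain in follow-up. About 7% relative dilution is a ceiling for the case of 14% stopping evenly with all retained. It would be smaller if fewer stopped or some left, and larger if stops clustered early. The text should be corrected before unblinding.

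**What to change.** Use one definition in protocol 8.4 and SAP 6.1.2:

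compliance (%) = 100 × capsules taken / capsules scheduled at the subject's assigned dose level (6, 8 or 10 per day after titration), from first dose to the planned Week 96 date.

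Then:

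1. State that the last assigned level is carried forward after a permanent stop. Without this, scheduled capsules after the stop could be read as zero, and the score would return to 100%.
2. State before unblinding how protocol-directed laboratory holds (protocol 8.6.2 and 8.6.3) are counted in the denominator.
3. Clarify in SAP 6.1.2 that the reference to randomization means treatment arm, not a fixed 10 capsules per day.
4. Reconcile the assessment weeks in protocol 8.4 with the Week 48 compliance check in 8.8.1.2.

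The cost is wording in two documents. Protocol 9.6 already puts dosing start and stop dates, dose level, and capsules dispensed and returned on the case report form. The per-protocol set becomes somewhat smaller. Removing early stoppers also selects on tolerance, so this analysis should continue to be read beside the mITT result.

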8.5. Randomization and Blinding

The study will consist of a screening phase (up to 45 days), followed by a double-blind treatment phase (96 weeks) and a follow-up visit (4 weeks after the 96 week visit). Following the screening phase, subjects who continue to meet entry criteria will be randomly assigned to one of two treatment groups: MN-166 100 mg/d or matching placebo. A total of 250 subjects, aged 21 to 65 years, will be enrolled and randomized into one of two treatment groups (MN-166 vs. placebo) in a 1:1 ratio. Randomization of subjects will be stratified by immunomodulating therapy status (IFN/GA vs. no DMT), and disease status (PPMS vs. SPMS). The NeuroNEXT DCC will generate a randomization table for each of the strata using a permuted block design with random block sizes.

8.6. Dosing Guidelines

8.6.1. Treatment Phase

Capsules containing either MN-166 (10 mg capsules) or matching-placebo will be used. At the Baseline Visit (Day 1), subjects will be instructed to take 3 capsules of study medication in the evening. Although the study drug can be taken in a fasted or fed state, subjects will be instructed to take study medication with food or within an hour of eating to improve gastrointestinal tolerability. Starting from Day 2, subjects will be instructed to take 3 capsules of study medication twice daily during the first 14 days and 5 capsules twice a day thereafter (or as directed by Investigator) once in the morning (e.g., between approximately 6-9 AM) and once in the evening (e.g., approximately 12 h later, which would be approximately 6-9 PM), by mouth. The investigator may also choose to administer the total daily dose of study medication on a three-times a day regimen to help reduce side effects.

If a subject forgets to take their AM or PM study drug dose at the assigned time (between 6-9 AM and PM), subjects will be allowed to take their medication up to 12 PM or 12 AM, respectively. Beyond this time, subjects will be instructed to skip the dose and take the next dose at their regularly scheduled time.

8.6.2 Dosing Interruption for Abnormal Laboratory Values

Laboratory tests should be repeated within two weeks after any of the following laboratory values are met:

- AST or ALT or ALP or T.bil > 3x upper limit of normal (ULN)
- GGT \geq 4 x ULN
- Creatinine > 1.2 x ULN
- White blood cell count < 2500/mm³
- Platelet count < 75,000/ mm³

If after repeat testing the laboratory value is still outside the above limits, then the subject should stop study medication. While dosing is withheld, subjects will continue tests and assessments according to the schedule defined in the protocol (and may also undergo additional assessments to evaluate the laboratory abnormality as per the Investigator's standard practice). In addition,

subjects must have the abnormal laboratory result rechecked at least every 2 weeks (rechecks will be run at the central laboratory) until resolution or stabilization of the laboratory value.

After laboratory values return within normal limits, resumption of blinded study treatment is to be considered on a case by case basis and must be discussed with the Independent Medical Monitor.

8.6.3 Subsequent Additional Laboratory Abnormalities

Subjects who subsequently develop the same abnormal laboratory value at any other time must permanently discontinue dosing with study treatment (i.e., only one dosing interruption is allowed for the same lab abnormality). However, subjects who subsequently experience a different laboratory abnormality can have study treatment withheld again for a different laboratory abnormality. However, only two dosing interruptions are allowed for each subject. Any subject who experiences a third abnormal laboratory tests as defined in Section 8.6.2 must permanently discontinue study treatment.

8.7. Written Informed Consent

Each subject is required to provide written informed consent prior to undergoing any study procedures. A copy of the signed and dated informed consent (in a language in which the subject is fluent) is required to be given to the subject. If a subject withdraws consent, data collected up to the time of discontinuation will be used to evaluate study results.

During the consent process, subjects will be informed that there is an FDA-approved treatment option available (i.e., mitoxantrone) for secondary progressive multiple sclerosis.

8.8. Assessments

Table 1: Schedule of Assessments

Table 2: Schedule of Unplanned Procedures and Assessments

Figure 12: Study Design

Visits Week 4, 8, 24, 48, 72, and 96 will have a window of ± 5 days. Safety visits conducted at Week 12, 36, 60, 84 and 100 will have a window of ± 14 days. (See Table 1 Schedule of Assessments)

Clinical laboratory evaluations will be performed by a central laboratory. All clinical and laboratory evaluations, procedures related to inclusion/exclusion criteria, or performed during treatment must be reviewed, initialed and dated by the Principal Investigator or appropriate designee listed on Form FDA 1572.

8.8.1. Assessments by Visit

The following is a summary of assessments by study visit:

8.8.1.1. Screening

Study Visit 1

- Informed consent

- Inclusion/Exclusion
- Medical history, MS history
- Physical examination
- Height/body weight
- Vital signs
- Prior/concomitant medication review
- Brief Pain Inventory (BPI)
- Cognitive tests [Symbol Digit Modalities Test (SMDT) and the Selective Reminding Test (SRT)]
- Short Form-36 Health Survey (SF-36)
- Multiple Sclerosis Impact Scale-29 (MSIS-29)
- EuroQoL 5 Dimensions (EQ-5D)
- Beck Depression Inventory-Fast Screen (BDI-FS)
- Hematology, chemistry, lipid profile, and urinalysis labs
- Serum biomarker samples
- Serum β -hCG (Serum pregnancy test) (in females)
- Electrocardiogram (12-lead ECG)
- Multiple Sclerosis Functional Composite (MSFC)
- Expanded Disability Status Scale (EDSS) by blinded neurologist
- Brain MRI*
- Optical Coherence Tomography (OCT)
- Lumbar puncture (optional)**

*MRI must be approved by the MRI Reading Center prior to randomization.

**Screening LP can be performed anytime between Screening Visit (inclusive) and Baseline Visit (inclusive), but prior to taking study drug. If MRI is done after screening LP, it must be at least 3 days after screening LP.

